### 16.5 Data & Safety Monitoring:

16.51 The principal investigator(s) and the study statistician will review the study at least twice a year to identify accrual, adverse event, and any endpoint problems that might be developing. The Mayo Clinic Cancer Center (MCCC) Data Safety

Monitoring Board (DSMB) is responsible for reviewing accrual and safety data for this trial at least twice a year, based on reports provided by the MCCC Statistical Office.

#### 16.52 Adverse Event Stopping Rules

The stopping rules specified below are based on the knowledge available at study development. We note that the Adverse Event Stopping Rule may be adjusted in the event of either (1) the study re-opening to accrual or (2) at any time during the conduct of the trial and in consideration of newly acquired information regarding the adverse event profile of the treatment(s) under investigation. The study team may choose to suspend accrual because of unexpected adverse event profiles that have not crossed the specified rule below.

Accrual will be temporarily suspended to this study if at any time we observe events considered at least possibly related to study treatment (i.e. an adverse event with attribute specified as “possible,” “probable,” or “definite”) that satisfy one of the following:

- if 2 or more patients in the first 6 treated patients experience a grade 4 or higher non-hematologic adverse event at least possibly related to treatment.
- if after the first 6 patients have been treated, 40% of all patients experience a grade 4 or higher non-hematologic adverse event at least possibly related to treatment.

We note that we will review Grade 4 and 5 adverse events deemed “unrelated” or “unlikely to be related”, to verify their attribution and to monitor the emergence of a previously unrecognized treatment-related adverse event.

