### 10.32 EXPECTED Serious Adverse Events: Protocol Specific Exceptions to Expedited Reporting

For this protocol only, the following Adverse Events/Grades are expected to occur within this population and do not require Expedited Reporting. These events must still be reported via Routine Reporting (see Section 10.6).\*

\*Report any clinically important increase in the rate of a serious suspected adverse reaction (at your study site) over that which is listed in the protocol or investigator brochure as an expedited event.

\*Report an expected event that is greater in severity or specificity than expected as an expedited event.

CTCAE System Organ Class (SOC)	Adverse event/ Symptoms	CTCAE Grade at which the event will not be expeditedly reported.
Blood and lymphatic system disorders	Anemia	≤ Grade 4
Gastrointestinal	Diarrhea	≤ Grade 3
	Nausea	≤ Grade 3
	Vomiting	≤ Grade 3
General disorders and administrations site conditions	Fatigue	≤ Grade 3
Investigations	Lymphocyte count decreased	≤ Grade 4
	Neutrophil count decreased	≤ Grade 4
	Platelet count decreased	≤ Grade 4
	White blood cell count decreased	≤ Grade 4

 These exceptions only apply if the adverse event does not result in hospitalization. If the adverse event results in hospitalization, then the standard expedited adverse events reporting requirements must be followed.

Specific protocol exceptions to expedited reporting should be reported expeditiously by investigators **ONLY** if they exceed the expected grade of the event.

The following hospitalizations are not considered to be SAEs because there is no “adverse event” (*i.e.*, there is no untoward medical occurrence) associated with the hospitalization:

- Hospitalizations for respite care
- Planned hospitalizations required by the protocol
- Hospitalization planned before informed consent (where the condition requiring the hospitalization has not changed post study drug administration)
- Hospitalization for elective procedures unrelated to the current disease and/or treatment on this trial
- Hospitalization for administration of study drug or insertion of access for administration of study drug
- Hospitalization for routine maintenance of a device (*e.g.*, battery replacement) that was in place before study entry

- Hospitalization, or other serious outcomes for signs and symptoms of progression of the cancer.]

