## 10.6 Required Routine Reporting

### 10.61 Baseline and Adverse Events Evaluations

Pretreatment symptoms/conditions to be graded at baseline and adverse events to be graded at each evaluation.

Grading is per CTCAE v4.0 **unless** alternate grading is indicated in the table below:

CTCAE SYSTEM/ORGAN/CLASS	Adverse event/Symptoms	Baseline	Each evaluation
Blood and lymphatic system disorders	Febrile neutropenia	X	X
Gastrointestinal Disorders	Baseline # of stools	X	
	Constipation		X
	Diarrhea		X
	Nausea	X	X
	Vomiting	X	X
General disorders and administration site conditions	Fatigue	X	X
Infections and infestations	Sepsis	X	X
Investigations	Creatinine increased	X	X
	Neutrophil count decreased	X	X
	Platelet count decreased	X	X
Skin and subcutaneous tissue disorders	Rash, maculo-papular	X	X

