**Rare known potential toxicities, <0.1% (Limited to important or life-threatening):**

Blood and lymphatic system disorders: immune thrombocytopenic purpura, hemolytic anemia  
Immune system disorders: sarcoidosis  
Nervous system disorders: Guillain-Barre syndrome, myasthenic syndrome  
Gastrointestinal disorders: small intestinal perforation  
Skin and subcutaneous tissue disorders: toxic epidermal necrolysis, Stevens-Johnson syndrome, erythema nodosum

The risk profile for pembrolizumab also includes two important potential risks: a) myasthenic syndrome, and b) an increased risk of severe complications (such as early severe graft versus host disease and venoocclusive disease) of allogeneic transplant in patients with hematologic malignancies who have previously been treated with PD-1 inhibitors.

Patients with multiple myeloma who were treated with pembrolizumab in combination with either pomalidomide or Lenalidomide and dexamethasone, had an increased number of serious side effects and deaths as compared to patients who received only dexamethasone and either pomalidomide or Lenalidomide. The benefit-risk profile is unfavorable for the combination of pembrolizumab, pomalidomide, and dexamethasone in relapsed refractory multiple myeloma, and the combination of pembrolizumab, Lenalidomide, and dexamethasone in newly diagnosed treatment-naïve multiple myeloma.

Post marketing reports identified Vogt-Koyanagi-Harada syndrome and hemophagocytic lymphohistiocytosis.

15.28 **Drug procurement:** Pembrolizumab will be provided free of charge to study participants by Merck.

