### 16.4 Early Safety Analysis

An early safety analysis will be performed after the first 6 patients have been accrued to the study and observed for at least 42 days. Accrual will be temporarily halted while these patients are evaluated. If 2 or more of the first 6 patients experience a DLT as defined below, then accrual to the study will continue to be temporarily halted while the study team determines if changes to the dosing schedule are warranted.

Toxicity will be measured per NCI-CTCAE version 4. DLT is defined as an adverse event occurring during the first cycle of treatment that is possibly, probably, or definitely related to study treatment and that meets one of the following:

- Any  $\geq$ Grade 4 neutrophil count decrease or platelet count decrease that persists  $>7$  days
- Any  $\geq$ Ggrade 3 infections
- $\geq$ Grade 3 erythema multiforme, ulceration, or urticarial that does not resolve to  $\leq$ Grade 2 within 3 weeks
- $\geq$ Grade 3 bronchial obstruction, pneumonitis, or wheezing
- $\geq$ Grade 3 allergic reaction or autoimmunity
- All other  $\geq$ Grade 3 non-hematologic toxicities (with the exception of electrolyte abnormalities that are reversible and asymptomatic) that does not resolve to  $\leq$ Grade 2 in  $\leq$ 72 hours despite optimal supportive medications

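### A treatment-related death coded only to a hematologic term does not count toward accrual suspension in Section 16.52 and, depending on coding, may also miss the DLT list in Section 16.4

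*Combined protocol and SAP*

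**What the plan says.** Section 16.52 of the combined protocol and SAP has two numeric triggers for temporary suspension of accrual, both confined to events at least possibly related to treatment. The early one applies "if 2 or more patients in the first 6 treated patients experience a grade 4 or higher non-hematologic adverse event at least possibly related to" the study drugs. The later one applies "if after the first 6 patients have been treated, 40% of all patients experience a grade 4 or higher non-hematologic adverse event". Neither mentions Grade 5 events or deaths separately.

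Section 16.4 sets an early safety analysis in the first six patients, with accrual halted while they are evaluated and kept halted if two or more have a DLT in cycle 1. The one item written for blood counts is a Grade 4 or worse "neutrophil count decrease or platelet count decrease that persists" for more than 7 days. The catch-all item covers other "non-hematologic toxicities (with the exception of electrolyte abnormalities that are reversible and asymptomatic"). Separate items cover infection and "allergic reaction or autoimmunity", each at Grade 3 or worse.

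Three other places bear on what counts as hematologic:
- Section 10.61 files "Febrile neutropenia" under the blood and lymphatic class.
- Section 15.27 lists "Blood and lymphatic system disorders: immune thrombocytopenic purpura, hemolytic anemia" among rare risks of pembrolizumab, and Sections 9.9b and 15.17 name thrombotic thrombocytopenic purpura (TTP) as a rare risk of ixazomib.
- Section 10.32 opens its list of exceptions with "For this protocol only, the following Adverse Events/Grades are expected to occur within this population". The hematologic entries in that list (anemia and the four count decreases) stop at Grade 4.

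**The concern.** Leaving hematologic events out of a suspension rule is reasonable in relapsed myeloma, where deep falls in counts are expected and would trip the rule without signaling a new hazard. But the exclusion applies to every grade from 4 upward, so it removes deaths along with the expected falls. Section 10.32 concerns expedited reporting rather than suspension, but it shows where the protocol itself stops regarding hematologic events as expected, and that is below Grade 5.

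The DLT definition covers cycle 1 only and is applied to the first six patients. After that, Section 16.52 is the only numeric safety rule. Section 16.214 relies on the adverse event stopping rule when it justifies continuing accrual through the interim analysis. A rule given that role should not be blind to one class of related deaths.

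**Working it through.** **Step 1. Apply the rules as written.** Take deaths at least possibly related to treatment, in cycle 1, in one of the first six patients, with no other qualifying event.

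| Death coded to | 16.52 | 16.4 DLT list |
|---|---|---|
| TTP | not counted | no clear item |
| Anemia | not counted | no item |
| Platelet decrease, death within 7 days | not counted | duration not met |
| Febrile neutropenia, no documented infection | not counted | depends on the reading (below) |
| Immune thrombocytopenia or hemolysis | not counted | possibly, as autoimmunity |
| Infection | counted | counted |
| Hemorrhage | counted, as non-hematologic | catch-all item |

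In the count-decrease item, the 7-day condition may attach to neutrophils and platelets or to platelets alone. If to platelets alone, a Grade 4 neutrophil decrease recorded beside a fatal febrile neutropenia is itself a DLT. Section 16.52 still omits the death, and the TTP, anemia and early platelet cases remain. For deaths after patient 6 or after cycle 1, the last column no longer applies.

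**Step 2. Thresholds.** The plan gives no operating figures for either safety rule, so there is none to reproduce. The early rule needs 2 of 6. The later rule needs the smallest whole number at or above 0.40n: n = 7, 2.8, so 3; n = 14, 5.6, so 6; n = 37, 14.8, so 15; n = 41, 16.4, so 17.

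**Step 3. What the rule gains by counting these deaths.** Let q be the per-patient risk of a related, hematologic-coded death and p the per-patient risk of a related non-hematologic event of Grade 4 or above, with no overlap. Both are assumptions. The current rule responds to p only; the amended rule responds to p + q.

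With p = 0, the early rule alone gives P(at least 2 of 6) = 1 − (1 − q)^6 − 6q(1 − q)^5:
- q = 5%: 1 − 0.7351 − 0.2321 = 0.033
- q = 10%: 1 − 0.5314 − 0.3543 = 0.114

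An exact patient-by-patient recursion over both rules, up to the maximum of 41 patients, gives the chance of ever suspending:

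| p | q | current | amended |
|---|---|---|---|
| 0 | 2% | 0 | 0.006 |
| 0 | 5% | 0 | 0.033 |
| 0 | 10% | 0 | 0.116 |
| 5% | 2% | 0.033 | 0.061 |
| 5% | 5% | 0.033 | 0.116 |
| 5% | 10% | 0.033 | 0.231 |

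At p = 0 and q = 10%, the later rule adds only 0.116 − 0.114 = 0.002. Nearly all of the gain is in the first six patients.

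**The case against.** The strongest reply is that the gap matters little in practice. Accrual halts after patient 6 whatever the DLT count, so early deaths would be examined with enrollment already stopped. Deaths within 30 days of the last dose, and later related deaths, must be reported within 24 hours (10.52). The study team may suspend for unexpected event profiles that have not crossed the rule (16.52), adverse events are weighed in any decision to terminate (16.23), safety concerns can end the study (13.6), and the DSMB reviews at least twice a year (16.51). All of this stands as mitigation. None of it makes the rule count these deaths: each route is reporting, judgment or periodic review. The extra review of Grade 4 and 5 events promised in 16.52 is for those judged unrelated or unlikely to be related. At 2 to 3 patients a month (16.13), six months between reviews is 12 to 18 patients.

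It is also fair that the result depends on coding. The plan does not define hematologic, the rules count patients, and any concurrent related non-hematologic event of Grade 4 or above in the same patient would count. That limits how often the gap opens but does not close it.

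Two stronger readings are tempting, and the documents do not support them. A reader might measure the defect by the chance of seeing two or more such deaths among 37 patients. That is the wrong measure, because two of 37 is far below the 15 that the 40% rule needs even after amendment. A reader might also take the statement in 15.27 about more deaths with pembrolizumab plus pomalidomide or lenalidomide as evidence that deaths would fall in this gap. That section gives no cause of death and does not describe them as hematologic.

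**Conclusion.** The point holds as a defect in what a stated safety rule counts. Section 16.52 never counts a related death coded only to a hematologic term, and Section 16.4 may miss it as well, depending on coding and on the reading of the 7-day condition.

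With no other qualifying events, correcting the count moves the chance of suspension from 0 to about 3% at an assumed 5% death rate and about 12% at 10%. These rates are stress values. The documents give none for such deaths, put immune thrombocytopenic purpura and hemolytic anemia below 0.1% as events, and call TTP rare. At 2% the figure is 0.6%.

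It should not be inferred that the amended rule would suspend accrual after one such death, or that it would respond well to deaths accumulating late in the trial. With the thresholds unchanged it would do neither. This is an inexpensive improvement, and its benefit lies mostly in the first-six rule.

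**What to change.** In both bullets of Section 16.52, define the counted event as one at least possibly related to treatment that is either non-hematologic and Grade 4 or above, or Grade 5 in any system organ class. In Section 16.4, add a related Grade 5 event of any class to the DLT list. For deaths in cycle 1, that also makes the reading of the 7-day condition immaterial. Leave the 2-of-6 and 40% thresholds as they are.

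The cost is two short wording changes. No new data are needed, because deaths are already reported under 10.52 and 10.623. The downside is a slightly higher chance of a temporary suspension, arising only when a related death has occurred.

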#### 16.6 Results Reporting on ClinicalTrials.gov:

At study activation, this study will have been registered within the [REDACTED] website. The Primary and Secondary Endpoints along with other required information for this study will be reported on [REDACTED]. For purposes of timing of the Results Reporting, the initial estimated completion date for the Primary Endpoint of this study is 3 years after the study opens to accrual. The definition of “Primary Endpoint Completion Date” (PECD) for this study is at the time all patients registered have been observed for 12 months.

#### 16.7 Inclusion of Women and Minorities

16.71 This study will be available to all eligible patients, regardless of race, gender, or ethnic origin.

16.72 There is no information currently available regarding differential effects of this regimen in subsets defined by race, gender, or ethnicity, and there is no reason to expect such differences to exist. Therefore, although the planned analysis will, as always, look for differences in treatment effect based on racial and gender groupings, the sample size is not increased in order to provide additional power for subset analyses.

16.73 The geographical region served by MCCC has a population which includes approximately 3% minorities. Based on prior MCCC studies involving similar disease sites, we expect about 3-5% of patients will be classified as minorities by race and about 33% of patients will be women. Expected sizes of racial by gender subsets are shown in the following table:

**Accrual Estimates by Gender/Ethnicity/Race**

Ethnic Category	Sex/Gender			Total
	Females	Males	Unknown	
Hispanic or Latino	0	1	0	1
Not Hispanic or Latino	14	26	0	40
Ethnic Category: Total of all subjects*	14	27	0	41
Racial Category				
American Indian or Alaskan Native	0	0	0	0
Asian	0	0	0	0
Black or African American	1	1	0	2
Native Hawaiian or other Pacific Islander	0	0	0	0
White	13	26	0	39
Racial Category: Total of all subjects*	14	27	0	41

**Ethnic Categories:** **Hispanic or Latino** – a person of Cuban, Mexican, Puerto Rico, South or Central American, or other Spanish culture or origin, regardless of race. The term “Spanish origin” can also be used in addition to “Hispanic or Latino.”

**Not Hispanic or Latino**

**Racial Categories:** **American Indian or Alaskan Native** – a person having origins in any of the original peoples of North, Central, or South America, and who maintains tribal affiliations or community attachment.

**Asian** – a person having origins in any of the original peoples of the Far East, Southeast Asia, or the Indian subcontinent including, for example, Cambodia, China, India, Japan, Korea, Malaysia, Pakistan, the Philippine Islands, Thailand, and Vietnam. (Note: Individuals from the Philippine Islands have been recorded as Pacific Islanders in previous data collection strategies.)

**Black or African American** – a person having origins in any of the black racial groups of Africa. Terms such as “Haitian” or “Negro” can be used in addition to “Black or African American.”

**Native Hawaiian or other Pacific Islander** – a person having origins in any of the original peoples of Hawaii, Guam, Samoa, or other Pacific Islands.

**White** – a person having origins in any of the original peoples of Europe, the Middle East, or North Africa.

**17.0 Pathology Considerations/Tissue Biospecimens: None****18.0 Records and Data Collection Procedures****18.1 Submission Timetable**

Data submission instructions for this study can be found in the Data Submission Schedule.

**18.2 Event monitoring**

See [Section 4.0](#) and data submission table for the event monitoring schedule.

**18.3 CRF completion**

This study will use Medidata Rave for remote data capture (rdc) of all study data.

**18.4 Site responsibilities**

Each site will be responsible for insuring that all materials contain the patient's initials, MCCC registration number, and MCCC protocol number. Patient's name must be removed.

**18.5 Supporting documentation**

This study requires supporting documentation for evidence of response to study therapy and progression after study therapy (sCR, MRD negative, PD).

**18.6 Labelling of materials**

Each site will be responsible for insuring that all materials contain the patient's initials, MCCC registration number, and MCCC protocol number. Patient's name must be removed.

**18.7 Incomplete materials**

Any data entered into a form will result in that form being marked as "received." However, missing data will be flagged by edit checks in the database.

**18.8 Overdue lists**

A list of overdue materials is automatically available to each site at any time. The appropriate co-sponsor/participant will be responsible to submit the overdue material.

**18.9 Corrections forms**

If a correction is necessary the QAS will query the site. The query will be sent to the appropriate site to make the correction in the database and respond back to the QAS.

**19.0 Budget**

- 19.1 Costs charged to patient: routine clinical care, and dexamethasone
- 19.2 Tests to be research funded: None
- 19.3 Other budget concerns: Ixazomib to be provided to the patient by Takeda free of charge. Pembrolizumab to be provided to the patient by Merck free of charge.

### Appendix I    ECOG Performance Status

ECOG PERFORMANCE STATUS*	
Grade	ECOG
0	Fully active, able to carry on all pre-disease performance without restriction
1	Restricted in physically strenuous activity but ambulatory and able to carry out work of a light or sedentary nature, e.g., light house work, office work
2	Ambulatory and capable of all selfcare but unable to carry out any work activities. Up and about more than 50% of waking hours
3	Capable of only limited selfcare, confined to bed or chair more than 50% of waking hours.
4	Completely disabled. Cannot carry on any selfcare. Totally confined to bed or chair.
5	Dead

\*As published in Am. J. Clin. Oncol.:

The ECOG Performance Status is in the public domain therefore available for public use. To duplicate the scale, please cite the reference above and credit the [REDACTED]

From [REDACTED]

## Appendix II PATIENT MEDICATION DIARY

Name \_\_\_\_\_ Study ID \_\_\_\_\_

Please complete this diary on a daily basis. Write in the amount of the dose of Ixazomib and dexamethasone that you took in the appropriate "Day" box.

On the days that you do not take any study drug, please write in "0". If you forget to take your daily dose, please write in "0", but remember to take your prescribed dose at the next regularly scheduled time.

Please drink at least 6 to 8 cups of liquid per day to help drug absorption. Swallow pills whole, with water, and do not to break, chew, crush or open the pills. The study drugs should be taken on an empty stomach (no food or drink) at least 1 hour before or at least 2 hours after a meal. Each pill should be swallowed separately with a sip of water. A total of approximately 8 ounces (240 mL) of water should be taken with the pills.

If you experience any health/medical complaints or take any medication other than ixazomib or dexamethasone, please record this information.

Week of:

Study Drug	Day 1	Day 2	Day 3	Day 4	Day 5	Day 6	Day 7
Ixazomib							
Dexamethasone							

Week of:

Study Drug	Day 8	Day 9	Day 10	Day 11	Day 12	Day 13	Day 14
Ixazomib							
Dexamethasone							

Week of:

Study Drug	Day 15	Day 16	Day 17	Day 18	Day 19	Day 20	Day 21
Ixazomib							
Dexamethasone							

Week of:

Study Drug	Day 22	Day 23	Day 24	Day 25	Day 26	Day 27	Day 28
Ixazomib							
Dexamethasone							

Week of:

Study Drug	Day 29	Day 30	Day 31	Day 32	Day 33	Day 34	Day 35
Ixazomib							
Dexamethasone							

Week of:

Study Drug	Day 36	Day 37	Day 38	Day 39	Day 40	Day 41	Day 42
Ixazomib							
Dexamethasone							

Week of:

Study Drug	Day 43	Day 44	Day 45	Day 46	Day 47	Day 48	Day 49
Ixazomib							
Dexamethasone							

Week of:

Study Drug	Day 50	Day 51	Day 52	Day 53	Day 53	Day 55	Day 56
Ixazomib							
Dexamethasone							

Week of:

Study Drug	Day 57	Day 58	Day 59	Day 60	Day 61	Day 62	Day 63
Ixazomib							
Dexamethasone							

Week of:

Study Drug	Day 64	Day 65	Day 66	Day 67	Day 68	Day 69	Day 70
Ixazomib							
Dexamethasone							

Week of:

Study Drug	Day 71	Day 72	Day 72	Day 74	Day 74	Day 76	Day 77
Ixazomib							
Dexamethasone							

Week of:

Study Drug	Day 78	Day 79	Day 80	Day 81	Day 82	Day 83	Day 84
Ixazomib							
Dexamethasone							

My next scheduled visit is:

If you have any questions, please call:

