## 7.0 Protocol Treatment

### 7.1 Treatment Schedule

Cycle length: 84 days.

Agent	Route	Dose	Day	Retreatment
Ixazomib	PO	4 mg	1, 8, 15, 29, 36, 43, 57, 64, 71	Every 84 days
Pembrolizumab	IV	200mg	Day 1, 22, 43, 64	Every 84 days
Dexamethasone	PO	40 mg	1, 8, 15, 29, 36, 43 57, 64, 71	Every 84 days

7.2 For this protocol, the patient must return to the consenting institution (Mayo Clinic) for evaluation at least every 21 days ( $\pm$  1 day). Treatment by a local medical doctor (LMD) is not allowed. Note: If patient is stable after 2 cycles, physical exam can be reduced to Weeks 1 and 7 of each cycle.

7.3 Patients are allowed to collect stem cells after 1 cycle of initial therapy. Stem cells can be collected using standard institutional protocols. Any delay beyond 4 weeks should be discussed with the study PI prior to reinitiating protocol therapy.

7.4 Patients should be instructed to swallow ixazomib capsules whole, with water, and not to break, chew, or open the capsules. The ixazomib should be taken on an empty stomach (no food or drink apart from 240 mL of water), at least 1 hour before or no sooner than 2 hours after food. Each capsule should be swallowed separately with a sip of water. A total of approximately 240 mL (about 1 cup/8 oz) of water should be taken with the capsules.

Missed doses can be taken as soon as the patient remembers as long as the next scheduled dose is 72 hours or more away. Patients who vomit a dose after ingestion will not receive an additional dose, but should resume dosing at the time of the next scheduled dose.

Drug will be administered only to eligible patients under the supervision of the investigator or identified sub-investigator(s). The drug will be prepared under the supervision of a pharmacist, or appropriately qualified and trained personnel.

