### 15.3 Dexamethasone for Oral Administration (DXM)

15.31 **Background:** Dexamethasone is an adrenal corticosteroid compound. Dexamethasone decreases inflammation by suppression of neutrophil migration, decreased production of inflammatory mediators, and reversal of increased capillary permeability; suppresses normal immune response. Dexamethasone's mechanism of antiemetic activity is unknown.

15.32 **Formulation:** Commercially available for oral administration as:  
Tablets [scored]: 0.5 mg, 0.75 mg, 1 mg, 1.5 mg, 2 mg, 4 mg, and 6 mg  
Solution, oral: 0.5 mg/mL (500 mL)  
Solution, oral concentrate: Dexamethasone Intensol: 1 mg/mL (30 mL)

15.33 **Preparation, storage, and stability:** Refer to package insert for complete preparation and dispensing instructions. Store oral tablets at room temperature between 20°C to 25°C (60°F to 77°F). Protect from moisture. Dispense in a well-closed, light-resistant container as defined in the USP/NF. Store oral liquid at room temperature, do not freeze. Do not use if solution contains a precipitate. Refer to commercial package for drug expiration date.

15.34 **Administration:** Refer to the treatment section for specific administration instructions. May be taken with meals to decrease GI upset.

15.35 **Pharmacokinetic information:**  
**Onset of action:** Prompt  
**Duration of metabolic effect:** 72 hours  
**Metabolism:** Hepatic  
**Half-life elimination:** Normal renal function: 1.8-3.5 hours; **Biological half-life:** 36-54 hours  
**Time to peak, serum:** Oral: 1-2 hours  
**Excretion:** Urine and feces

15.36 **Potential Drug Interactions:**  
**Cytochrome P450 Effect: Substrate of CYP3A4 (major); Induces CYP2A6 (weak), 2B6 (weak), 2C8 (weak), 2C9 (weak), 3A4 (strong)**  
**Increased Effect/Toxicity:** Aprepitant, azole antifungals, calcium channel blockers, cyclosporine, estrogens, and macrolides may increase the serum levels of corticosteroids. Corticosteroids may increase the hypokalemic effects of amphotericin B or potassium-wasting diuretics (loop or thiazide); monitor. Refer to the package insert for a listing of other drugs.  

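### For a forgotten ixazomib dose, the patient diary says to wait for the next scheduled dose, while Section 7.4 allows a late dose if the next is at least 72 hours away

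*Combined protocol and SAP*

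**What the plan says.** Three places in the combined protocol and SAP deal with a missed oral dose.

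- **Section 7.4** opens with ixazomib: "Patients should be instructed to swallow ixazomib capsules whole, with water, and not to break, chew, or open the capsules". Its second paragraph then gives the rule for missed doses: "Missed doses can be taken as soon as the patient remembers as long as the next scheduled dose is 72 hours or more away". A vomited dose is treated separately: "Patients who vomit a dose after ingestion will not receive an additional dose, but should resume dosing at the time of the next scheduled dose".
- **Section 7.5** covers dexamethasone and rules out making up a missed dose.
- **Appendix II**, the patient diary, has a row for each of the two drugs on every day of the cycle and one instruction for both. A patient who forgets a dose enters 0, "but remember to take your prescribed dose at the next regularly scheduled time". The diary mentions no 72-hour allowance and does not separate the drugs.

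Two further passages bear on how the diary is used. Footnote 6 to the Section 4.1 schedule requires it to be completed in line with the protocol and returned. Section 15.13 has ixazomib dispensed for use at home and asks that patients receive full dosing instructions.

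**The concern.** The diary is a dosing instruction that the patient keeps at home, and for ixazomib it differs from the treatment section. For a forgotten dose it gives the outcome that Section 7.4 reserves for a vomited dose, namely to wait for the next scheduled one. For a missed dose, Section 7.4 provides something else.

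What is at stake is uniform conduct and a readable dose record. A patient who relies on the diary and a patient who was told the Section 7.4 rule at the clinic can handle the same lapse differently. One takes a late dose and the other records 0. Someone reading the returned diaries cannot tell whether a 0 on a dosing day means that the window had closed or that the patient did not know it existed.

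**Working it through.** The plan states no figure on this point, so there is none to reproduce. The check compares the texts and then works out how often they can diverge.

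**Step 1: compare the rules by drug.**

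| Forgotten dose of | Treatment section | Diary | Match? |
|---|---|---|---|
| Dexamethasone | 7.5: not made up | Enter 0, wait for next scheduled time | Yes |
| Ixazomib | 7.4: may be taken late if the next dose is at least 72 h away | Enter 0, wait for next scheduled time | Only within 72 h of the next dose |

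**Step 2: length of the late-dose window for ixazomib.** The inputs are the dosing days in Section 7.1 (1, 8, 15, 29, 36, 43, 57, 64, 71), the 84-day cycle, and the 72-hour limit in Section 7.4. The next cycle is assumed to start on time, so the dose after Day 71 falls on Day 85.

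Window = (gap to next dose in days × 24) − 72 hours.

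- Gap of 7 days, after Days 1, 8, 29, 36, 57 and 64: 7 × 24 − 72 = 96 h = 4 days.
- Gap of 14 days, after Days 15, 43 and 71: 14 × 24 − 72 = 264 h = 11 days.

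As a check, 6 × 4 + 3 × 11 = 57 days lie inside a window and 9 × 3 = 27 days lie outside, and 57 + 27 = 84. The two instructions can therefore diverge after any of the nine doses. They coincide only in the last three days before the next dose.

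**Step 3: size for one patient.** At a constant dose level, one dose is 1/9 = 11% of the cycle's ixazomib. This applies only if the patient forgets a dose, remembers it inside the window, and then waits because the diary says so.

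**Step 4: size for the trial.** This needs the proportion of doses forgotten, which the documents do not give. Purely as an assumption, if 1% to 5% of ixazomib doses were forgotten, at most 1% to 5% of planned ixazomib could be affected. The share would be smaller if some doses are remembered too late or if patients follow clinic advice. The documents offer nothing to narrow that range or to link it to response.

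**The case against.** The strongest reply is that Section 7.4 is permissive. A missed dose can be taken late, but nothing says that it must be, so a patient who follows the diary breaches nothing. This stands: the diary leaves out an option and does not order something the protocol forbids. It also stands that the diary is right for dexamethasone.

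The diary is not the only source of instruction either. Section 15.13 calls for full instructions to the patient and for reconciliation when the patient returns for the next cycle, and Section 7.2 brings patients back at least every 21 days. These safeguards reduce the problem. They do not remove it, because none of them restates the 72-hour rule or says which text prevails.

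A reader might also infer two further contradictions in the diary, and the documents do not support them.

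- **Food.** The diary says of both drugs: "The study drugs should be taken on an empty stomach". Section 15.34 says of dexamethasone: "May be taken with meals to decrease GI upset". The second is optional wording and refers to the treatment section for specifics, and Section 7.5 gives no food instruction. Taking dexamethasone fasting therefore violates no passage.
- **Daily wording.** The diary speaks of a daily dose although neither drug is taken daily. It also tells patients to enter 0 on days without study drug, so it plainly expects such days. The phrase is loose, but no dosing error follows from it.

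**Conclusion.** The inconsistency is real and confined to ixazomib. The diary and Section 7.4 give different instructions for a forgotten dose, and the difference can arise at all nine doses of a cycle, within a window of 4 days (six doses) or 11 days (three doses). For an affected patient one dose is 11% of the cycle's ixazomib.

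This rests on two assumptions: that the missed-dose sentence in Section 7.4 concerns ixazomib, as that section's opening and the separate rule in Section 7.5 indicate, and that cycles start on schedule.

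A reader might go on to infer that delivered dose intensity will fall below plan and weaken the response endpoint. The documents do not support that. They give no missed-dose rate, and calling the diary's outcome a loss against plan presumes that Section 7.4 is the rule intended. Section 16.3 lists no analysis of exposure, and the endpoint definition, decision rule and operating characteristics in Sections 16.1 and 16.2 are untouched. The point is a correction to a patient-facing instruction and does not affect the design.

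**What to change.** Reconcile Section 7.4, Section 7.5 and Appendix II drug by drug. The clinical lead should confirm which missed-dose instruction stands for ixazomib; this review takes no position on that. Then reissue the diary with a separate missed-dose line for each drug, worded to match the treatment sections. If late ixazomib doses remain allowed, add a line on how to record them. The diary already has a box for every day of the cycle, so the layout can stay as it is.

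The daily wording and the shared food instruction (compare Section 15.34) can be clarified in the same revision, as matters of wording only.

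The cost is one revised diary page, plus a matching edit to Section 7.4 if the clinical lead decides that the diary's instruction should stand. Sample size, analysis and visit schedule do not change.
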